8.4.3. Long-Term Extension Period Efficacy Endpoints (Part B)

The analysis details for the LTE Period will be included in the SAP.

8.4.4. Continued Long-Term Extension Period Efficacy Endpoints (Part C)

The analysis details for the Continued LTE Period will be included in the SAP.

8.4.5. Safety Analyses

Safety is measured by the severity and number of TEAEs and TESAEs, change from baseline in clinical laboratory tests, physical examination, vital signs, and 12-lead ECGs during the Treatment Period.

Baseline is defined as the last value measured prior to first dose intake (vital signs, 12-lead ECG, laboratory parameters, C-SSRS), unless otherwise specified.

The following have been defined as parameters regarding safety and tolerability:

- Change from baseline to each scheduled timepoint up to EOS for vital signs
- Change from baseline to each scheduled timepoint up to EOS for 12-lead ECG parameters
- Change from baseline to each scheduled timepoint up to EOS for clinical laboratory tests
- Changes from baseline in C-SSRS scores
- Treatment-emergent AEs up to EOS
- Treatment-emergent AEs leading to premature discontinuation of study drug
- Treatment-emergent SAEs up to EOS

All safety data will be populated in the individual eCRFs. Safety data, including dosing dates and times, will be listed by subject.

All AEs and SAEs will be coded using the most current version of MedDRA available at PTC and summarized by treatment for the number of subjects reporting the TEAEs/TESAEs and the number of TEAEs reported.

The TEAEs/TESAEs are tabulated by System Organ Class (SOC) and individual Preferred Terms within each SOC by treatment group. The number and percentage of subjects who experienced AEs coded with the same Preferred Term and SOC will be summarized by treatment group (in descending order according to the incidence in the investigational study drug group). Adverse events will also be tabulated by severity and by relationship to study drug. Summary tables will be accompanied by individual subject listings broken down by treatment group, including predose events.

Reasons for death will only be listed. Reasons for premature discontinuation of study drug will be listed and summarized by frequency tables.

Safety data, including 12-lead ECGs, vital signs assessments, and clinical laboratory results, will be summarized at each timepoint using mean, median, standard deviation, minimum, maximum, number of available observations, and change from baseline. Individual subject listings of 12-lead ECG data, vital signs data, laboratory measurements, and C-SSRS scores will be provided.

Standard numeric laboratory parameters are presented in the units supplied. If needed, a conversion will be made to standard units.

Quantitative safety data as well as the difference from baseline, when appropriate, will be summarized using the appropriate descriptive statistics.

Concomitant medications will be listed by subject and coded using the most current version of World Health Organization (WHO) drug dictionary available at PTC.

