| Modified Norris Scale | | | Х | | | | Х | | | Х | | Х |
| ALSAQ-40 | | | Х | | | | Х | | | Х | | Х |
| EQ-5D-5L | | | Х | | | | Х | | | Х | | Х |
| C-SSRS ^v | Х | Х | Х | | Х | Х | Х | Х | Х | Х | Х | Х |
| Study drug dispensation | | | Х | | | | Х | | | | | |
| Adverse events | Х | Х | Х | Х | Х | Х | Х | Х | Х | Х | Х | Х |
| Prior/concomitant medications | Х | Х | Х | Х | Х | Х | Х | Х | X | Х | Х | Х |
| Mammogram ^w | Х | | | | | | | | | Х | | Xx |

| | | | | | | Treatme | ent Period | | | | EOS/ FU | Early Termination |
|---|--------------------|---------|-----------------------|--------|-------------|-----------|-----------------|---------|---------|----------------------------------|----------------|----------------------|
| | | | | | | (24 W) | | | | '0 | Termination | |
| Study Day | Screening | Day -28 | Day 1 | Day 14 | Day 29 | Day 57 | Day 85 | Day 113 | Day 141 | Day 169 | Day 197 | |
| | (-56 Days) (±5) | (±3) | (-3) ^a | (±3) | (±3) | (±3) | (±3) | (±3) | (±3) | (±3) | (±3) | |
| | | | Baseline ^a | | | | | | | End of Treatment ^b | Follow- Up° | ET⁴ |
| | | | | PK S | Sub-Study A | Assessmen | ts ^y | | I | | | |
| Telephone call or in- person visit | IP | IP | IP | PC/IH | IP | PC/IH | IP | PC | PC | IP | PC | IΡ |
| Serial PTC857 PK blood sampling | | | Х | | Х | | Х | | | Х | | Х |
| Riluzole PK blood sampling | | Х | Х | | Х | | | | | | | |
| Edaravone PK blood sampling | | Х | Х | | Х | | | | | | | |
| Sodium phenylbutyrate/taurursod iol PK sampling | | Х | Х | | Х | | | | | | | |
| CSF for PK ^z | | | Х | | Х | | | | | Х | | Х |
| Additional ECGs | | | Х | | Х | | | | | | | |

Abbreviations: ALS, amyotrophic lateral sclerosis; ALS CBS, ALS Cognitive Behavioral Screen; ALSAQ-40, ALS Assessment Questionnaire; ALSFRS-R, ALS Functional Rating Scale-Revised; BMI, body mass index; COVID-19, coronavirus disease 2019; CSF, cerebrospinal fluid; C-SSRS, Columbia-Suicide Severity Rating Scale; ECG, electrocardiogram; EOS, end of study; EQ-5D-5L, five-level European quality of life five-dimensional questionnaire; ET, early termination; FSH, follicle-stimulating hormone; FU, follow-up; ICF, Informed Consent Form; IH, in-home; IP, in-person; LTE, Long-Term Extension; p75NTR, p75 neurotrophin receptor; PC, telephone call; PCR, polymerase chain reaction; PFT, pulmonary function test; PI, Principal Investigator; PK, pharmacokinetic; SAE, serious adverse event

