- ^u Pulmonary function tests will assess slow vital capacity and Sniff Nasal Inspiratory Pressure. Forced vital capacity, vital capacity, forced expiratory volume, and maximum inspiratory pressure will not be measured. Refer to the laboratory manual for specific requirements at Screening. Oxygen saturation, respiratory rate, and heart rate will be assessed in both upright and supine positions. The Sniff Nasal Inspiratory Pressure test will assess nasal pressure in each unilaterally occluded nostril during a maximal sniff to assess inspiratory muscle strength.

- ^v During the Screening Visit (Day -56), the "baseline" version of the C-SSRS will be administered. At all other visits, the "since last visit" version will be administered.
- w Mammograms to be conducted for female subjects only. A mammogram is not required during the Screening Period if the subject has had a negative breast cancer imaging status (ie, not considered clinically abnormal and/or requiring further evaluation/treatment) within 6 months prior to the Screening Visit. If clinically indicated, an ultrasound or MRI may also be conducted for breast cancer imaging, per the investigator's discretion. If a subject cannot complete the Screening mammogram or any necessary follow-up procedures during the Screening Period, the Screening Period may be extended after discussion and agreement with the medical monitor.
- ^x Women who have been exposed to study drug for at least 3 months and discontinue treatment before reaching the Day 169 Visit will have breast cancer surveillance imaging performed at the Early Termination Visit. Women who have been exposed to study drug for <3 months and discontinue treatment before reaching the Day 169 Visit may have breast cancer surveillance imaging performed at the investigator's discretion.
- ^y The following additional procedures will be conducted only in subjects taking part in the optional PK Sub-Study:
 - Blood samples for riluzole, edaravone, and/or sodium phenylbutyrate/taurursodiol PK will be collected at Day -28 predose (prior to the first dose of riluzole, edaravone, and/or sodium phenylbutyrate/taurursodiol on Day -28) and 1 hour (±15 minutes) post-dose. Subjects should be instructed not to take riluzole, edaravone, and/or sodium phenylbutyrate/taurursodiol on Day -28 prior to the study visit.

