7. STUDY ASSESSMENT AND PROCEDURES

The scheduled timepoints and study parameters are delineated in the Schedule of Assessments (Table 1 [Part A], Table 2 [Part B], and Table 3 [Part C]).

In case several study procedures are scheduled at the same timepoint, the following sequence should be followed predose: 12-lead ECG, vital signs, PK blood sampling, and blood sampling for clinical laboratory tests. Likewise, for post-dose, the following sequence should be followed: 12-lead ECG, vital signs, PK blood sampling, and blood sampling for clinical laboratory tests.

During the Day 1, Day 85, and Day 169 Visits, the following testing clinical measures should be performed predose: ALSFRS-R, PFTs, ALS CBS, Modified Norris Scale, C-SSRS, and ALSAQ-40. The ALSFRS-R should be the first test performed; all other tests may be performed in any order.

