7.2.7. Columbia-Suicide Severity Rating Scale

The C-SSRS is a questionnaire that prospectively assesses suicidal ideation and suicidal behavior. The C-SSRS, which uses a semi-structured interview to probe subject responses, will be administered by an individual who has received training and certification in its administration. During the Screening Visit (Day -56), the "baseline" version of the C-SSRS will be administered. This version assesses suicidal ideation and suicidal behavior during the subject's lifetime and during a predefined period. At all subsequent visits, the "since last visit" version will be administered.

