3.2.2. Baseline Definition and Change from Baseline

The Baseline Visit will be defined as Day 1 of the study. Unless otherwise stated, for each subject, baseline value of a parameter is defined as the last non-missing measurement taken at most one week prior to the first dose of study drug (including unscheduled assessments). If the last non-missing measurement and the date of first dose of study drug coincide, that measurement will be considered baseline, but AEs and medications commencing on the date of first dose of study drug will be considered post-baseline.

For the purposes of calculating summary statistics of the outcome measures, change from baseline will be derived as follows:

• Change from baseline = Post-baseline value – Baseline value

3.2.3. **Duration of Event**

Where the duration of an event is to be calculated, it will be derived as:

Duration (days) = (Event stop/end date – Event start date) + 1.

Duration (months) = Duration (days) / 30.4375

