- Counts and Percentage of Subjects with Suicidal Ideation, Suicidal Behavior, and Self-Injurious Behavior without Suicidal Intent Based on the C-SSRS by Treatment group at baseline.
- Counts and Percentage of Subjects with Suicidal Ideation, Suicidal Behavior, and Self-Injurious Behavior without Suicidal Intent Based on the C-SSRS by Treatment group during the double-blind treatment period.

- Counts and Percentage of Subjects with Suicide-Related Treatment Emergent Events Based on C-SSRS by Treatment group during the Double-Blind Treatment Period.
- Shift table of changes in C-SSRS categories (ideation, behavior, or neither) from baseline to through Week 24.
- Shift table in Changes in C-SSRS Suicidal Ideation scores from baseline to through Week 24 by Treatment.

All C-SSRS assessments will be listed.

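### The C-SSRS baseline is the Day 1 since-last-visit form alone, so suicidality recorded earlier in the run-in is left out of the baseline counts and shift tables

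*Protocol*

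**What the plan says.** **Schedule.** Protocol Table 1 places the C-SSRS at three visits before dosing (Screening at Day -56, Day -28 and Day 1) and at six on-treatment visits in Part A (Days 29, 57, 85, 113, 141 and 169). For Day 1, Day 85 and Day 169, Protocol section 7 requires that "the following testing clinical measures should be performed predose: ALSFRS-R, PFTs, ALS CBS, Modified Norris Scale, C-SSRS, and ALSAQ-40", so the Day 1 form precedes the first dose.

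**Form version.** Only Screening uses the form called the baseline version. Protocol section 7.2.7 says of it: "This version assesses suicidal ideation and suicidal behavior during the subject's lifetime and during a predefined period". For the rest, Table 1 footnote v states: "At all other visits, the 'since last visit' version will be administered".

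**Baseline rule.** Protocol section 8.4.5: "Baseline is defined as the last value measured prior to first dose intake (vital signs, 12-lead ECG, laboratory parameters, C-SSRS), unless otherwise specified". Part A SAP section 3.2.2: "baseline value of a parameter is defined as the last non-missing measurement taken at most one week prior to the first dose of study drug". Each rule allows for an exception stated elsewhere. SAP section 6.7 states none for the C-SSRS.

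**Outputs.** SAP section 6.7 plans counts at baseline, counts during the double-blind period, a table of treatment-emergent C-SSRS events, a shift table of ideation scores, and this category table: "Shift table of changes in C-SSRS categories (ideation, behavior, or neither) from baseline to through Week 24". It uses a subject's worst finding for the overall assessment of the double-blind period. It has no corresponding rule for the period before dosing.

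**The concern.** A last-value rule suits a measurement of current state, such as blood pressure. A since-last-visit questionnaire reports on an interval, so the last form says nothing about earlier intervals. Suicidality recorded at Day -28, or in the recent period of the Day -56 form, is collected but does not enter the analysis baseline.

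Take a subject with ideation at Day -56 and Day -28, none on Day 1, and the same ideation again at Day 57. At baseline this subject is classed as neither, with ideation score 0. The recurrence then appears as new ideation on treatment, although the trial's own data show that it pre-dated dosing.

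Change in C-SSRS is part of a named secondary safety endpoint (Protocol section 2.2.2). Some pre-existing ideation is plausible: no exclusion criterion is tied to a C-SSRS result, and SAP section 6.2.2 lists suicidal ideation among the terms it treats as indicative of ALS progression. Baseline tables that understate pre-existing suicidality make the on-treatment tables harder to read.

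**Working it through.** The plan gives no figure to reproduce, because the point concerns a definition. The check is to find which form the rules select and what period it covers.

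**Inputs (Protocol Table 1, counted in days before first dose).** Screening 56 ± 5, so 51 to 61. Day -28 ± 3, so 25 to 31. Baseline visit up to 3 days early, so 0 to 3. These ranges assume that the tabulated windows hold; footnote w allows some screening periods to be extended.

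**Which form qualifies.**
- SAP limit of 7 days: Screening (at least 51) fails, Day -28 (at least 25) fails, Day 1 (at most 3) passes.
- Protocol last-value rule: Day 1 is the latest pre-dose form.
- Both rules select Day 1.

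**What each form covers.**
- Day 1 form: nominally 28 days. Shortest 25 − 3 = 22; longest 31 − 0 = 31.
- Day -28 form: nominally 56 − 28 = 28 days. Shortest 51 − 31 = 20; longest 61 − 25 = 36. Not in baseline.
- Screening form: lifetime plus a recent period whose length is not given. Not in baseline.
- Nominal share of the run-in covered by the analysis baseline: 28/56 = 50%.

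**Consequence for each output.**
- Baseline counts: ideation or behavior reported only on the two earlier forms is absent.
- Shift tables: the baseline side is the Day 1 form, so a subject positive earlier and negative on Day 1 starts from neither, or score 0. A recurrence then shows as a shift if it falls within whatever on-treatment value the table uses.
- Treatment-emergent table: no C-SSRS rule is given. The general adverse-event definition in SAP section 6.2 (onset or worsening after first dose) would also count a recurrence, but this is an inference.

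**Size.** The documents give no rate of ideation, so the effect on the tables cannot be estimated. A purely hypothetical calculation shows how the rule works. Take a subject with recurrent pre-existing ideation and assume a probability p of reporting it on each form, independently between forms and equal on all of them. Let k be the number of pre-dose forms that count and let there be six on-treatment forms. The chance of being negative at baseline and positive at least once on treatment is (1 − p)^k × [1 − (1 − p)^6].

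| Assumed p | k = 1 (Day 1 only) | k = 3 (all pre-dose forms) |
|---|---|---|
| 0.3 | 0.700 × 0.882 = 0.62 | 0.343 × 0.882 = 0.30 |
| 0.4 | 0.600 × 0.953 = 0.57 | 0.216 × 0.953 = 0.21 |
| 0.5 | 0.500 × 0.984 = 0.49 | 0.125 × 0.984 = 0.12 |

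These values apply only to such a subject and also assume that any positive on-treatment form counts. They are not a forecast for the trial.

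**The case against.** The strongest objections, and what stands of each:

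- **The baseline form is arguable.** SAP section 6.7 calls the Day -56 form the baseline version and then plans counts at baseline, so a programmer could take Day -56 as the comparator. The ambiguity is real, but that is the name of a form. Reading it as the analysis baseline contradicts Protocol section 8.4.5 and the one-week limit. It would also bring lifetime history into baseline and could hide genuine new onset, which is the opposite error.
- **Treatment-emergent status is not shown to be wrong.** A reader might infer that recurrent ideation will definitely be counted as treatment-emergent. The documents do not support that: the SAP states no C-SSRS rule, and the table shells are in a separate document.
- **The comparison of 4 weeks with the worst of 24 weeks is not established for the shift tables.** The worst-finding rule is attached to the overall assessment. The shift-table wording leaves the on-treatment value unclear. The baseline side is affected either way.
- **The harm is limited.** Safety tables are descriptive, a randomized placebo arm is affected in the same way, the C-SSRS is outside the testing sequence in SAP section 4.6, and every assessment is listed. This stands. A reader might infer a biased treatment comparison; nothing in the documents shows one. The listings do not correct the summary tables, however.
- **Few subjects may be affected.** Exclusion criteria 3 and 4 let the investigator exclude significant psychiatric disease. This also stands, and is a further reason not to put a size on the effect.
- **Over-counting is the cautious direction for safety.** That is a fair preference, but a shift table should show change from what was known before dosing.

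**Conclusion.** The point holds for the baseline counts and both shift tables in SAP section 6.7. The stated rules select the Day 1 form, which covers nominally half of the run-in, and suicidality recorded only on the earlier pre-dose forms drops out of baseline. For the treatment-emergent table the same effect is possible but not established.

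The consequence is misclassification in descriptive safety tables in both arms, of a size that the documents do not allow one to estimate. The primary endpoint, alpha, power and sample size are untouched. The conclusion assumes that SAP section 3.2.2 governs the C-SSRS, since section 6.7 states no exception, and that the unseen table shells do not redefine baseline. It deserves correction because the rule is stated and unsuited to an interval-recall form, and because the data needed are already collected.

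**What to change.** In SAP section 6.7, and in Protocol section 8.4.5 for consistency:

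- Define the C-SSRS baseline as the worst ideation/behavior category over all pre-dose assessments: the recent period of the Day -56 form, Day -28 and Day 1. State the length of that recent period, which Protocol section 7.2.7 mentions without a length and SAP section 6.7 omits.
- Use this baseline for the baseline counts, both shift tables and the treatment-emergent table. Show lifetime history separately.
- Define a treatment-emergent C-SSRS event as one that is new or worse than this baseline.
- State whether the on-treatment side of the shift tables is the worst finding or the Week 24 form.

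In the Parts B/C SAP, section 6.8, the Part A baseline should not simply be carried over. Subjects randomized to placebo first receive PTC857 at Day 169. For them, use the worst finding over all assessments before the first PTC857 dose, including the placebo period. Otherwise ideation that first arose on placebo could look emergent on PTC857.

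The cost is a few lines of SAP text and one derivation, with no new data. The downside is that a recurrence of ideation that had resolved by Day 1 is no longer labelled new unless it is worse than before. For a subject with recurrent ideation this could be a substantial change in labelling, but every such event stays in the on-treatment counts and in the listings.

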8.4.6. Pharmacokinetic Analyses

The plasma PTC857, riluzole, edaravone, and/or sodium phenylbutyrate/taurursodiol concentrations, the PK parameters, and CSF exposure listed in Section 7.1.8.4 and Section 7.1.8.5 will be summarized using appropriate descriptive statistics, which will be fully outlined in the PK SAP.

8.5. Interim Analysis

No interim analysis is planned for this study.

9. DIRECT ACCESS TO SOURCE DATA/DOCUMENTS

In accordance with 21 Code of Federal Regulations Part 312.56 and/or relevant ICH guidelines, PTC or a designee will periodically inspect all eCRFs, study documents, research facilities, and clinical laboratory facilities associated with this study at mutually convenient times, before, during, and after completion of the study. As required by applicable regulations (FDA 2020), the monitoring visits provide PTC with the opportunity to evaluate the progress of the study; verify the accuracy and completeness of data in the eCRFs; ensure that all protocol requirements, relevant regulations, and investigator's obligations are being fulfilled; and resolve any inconsistencies in the study records. This includes inspection of all documents and records required to be maintained by the investigator, including but not limited to medical records (office, clinic, or hospital) for the subjects in this study. The names and identities of all research subjects will be kept in strict confidence and will not appear on eCRFs or other records provided to or retained by PTC. The investigator/institution guarantees direct access to source documents by PTC or a designee and appropriate regulatory authorities.

It is important that the investigator and relevant institutional personnel are available during the monitoring visits and possible audits, or inspections and that sufficient time is devoted to the process.

9.1. Study Monitoring

Before a potential investigational site can be selected to conduct the study, a representative of PTC or its designee will visit the investigational study site to:

- Determine the adequacy of the facilities
- Discuss with the investigator(s) and other personnel their responsibilities with regard to protocol adherence and the responsibilities of PTC or its representatives. This will be documented in a Clinical Study Agreement between PTC and the investigator

During the study, a monitor from PTC or representative will have regular contacts with the investigational site for the following:

- Provide information and support to the investigator(s)
- Confirm that facilities remain acceptable
- Confirm that the investigational team is adhering to the protocol, that data are being accurately recorded in the case report forms, and that investigational product accountability checks are being performed
- Perform source data verification. This includes a comparison of the data in the case report forms with the patient's medical records at the hospital or practice and other records relevant to the study. This will require direct access to all original records for each patient (eg, clinic charts)
- Record and report any protocol deviations not previously sent to PTC

 Confirm AEs and SAEs have been properly documented on eCRFs and confirm any SAEs have been forwarded to PTC and those SAEs that met criteria for reporting have been forwarded to the IRB/IEC

The monitor will be available between visits if the investigator(s) or other staff needs information or advice.

